5.3.1.1.5 Vital Signs

Body temperature and vital signs will be measured at the times indicated in the Study Activities Table ([Appendix C](#)).

Blood pressure and pulse rate are to be measured while the subject has been sitting for at least 5 minutes. Study staff should make efforts to measure on the same arm and with the same method, including recording of the arm and method in the subject's source documentation.

For visits in which both vital signs and blood sample(s) are collected, vital signs should be obtained prior to any blood collection.

5.3.1.1.6 Body Weight

Body weight will be measured at the times indicated in the Study Activities Table ([Appendix C](#)). The subject will wear lightweight clothing and no shoes during weighing.

5.3.1.1.7 Pregnancy Testing

WOCBP must have a negative urine pregnancy test result on Day 1. Pregnancy testing should be performed during treatment at the times indicated in the Study Activities Table ([Appendix C](#)), including at the last dose of study drug and for at least 20 weeks after the last dose of study drug. WOCBP must also have a negative urine pregnancy test result prior to any radiological procedures.

5.3.1.1.8 Neurological Examination

A neurological examination will be performed at the times indicated in the Study Activities Table ([Appendix C](#)). The neurological exam performed on Day 1 will serve as the baseline for clinical assessment. Symptoms identified on Day 1 will be recorded as adverse events for Study M15-562; new symptoms or current symptoms that change in severity or frequency after Day 1 will be recorded as adverse events for Study M15-563.

The neurological examination will assess:

- Mental Status – assessment of orientation, speech, and memory
- Cranial nerves – assessment of cranial nerves II – XII. This will include an assessment of supranuclear gaze palsy and slowing of vertical saccades.
 - Vertical supranuclear palsy will be established by neurological examination demonstrating a greater than 50% limitation of the range of voluntary gaze in the vertical plane, which is overcome by reflexive vestibular stimulation
 - Slowing of vertical saccades may be assessed by either of the two following methods:
 - Slowing of vertical saccades may be established by neurological examination of saccades toward a target held greater than 20 degrees from the position of primary gaze in the vertical plane. Slowing of vertical saccades will be defined as present when ocular movement is slow enough for the examiner to see its progress, rather than just its initial and final positions. A delay in initiation of saccades is not considered slowing.
 - Slowing of vertical saccades may be established using quantitative measurements of saccades, such as infrared oculography of adequate spatial and temporal resolution to resolve multiple saccades.
- Motor system – brief assessment of tone and strength, tremors
- Sensory system – brief assessment of light touch and temperature sensation
- Reflexes – assessment of deep tendon reflexes and plantar responses (Babinski sign)

- Coordination – assessment of upper and lower extremities, including assessment for tremor
- Gait – assessment of tandem gait (if clinically indicated and safe)
- Station – assessment of posture and stability as defined by the following:
 - If clinically indicated and safe, postural instability may be assessed by determining the impairment of postural reflexes on neurological examination (i.e., retropulsion with or without unaided recovery after a backward pull) in the absence of any other medical cause to explain this impairment (e.g., primary sensory deficit, vestibular dysfunction, pontine infarction, cerebellar syndrome, prominent upper or lower motor neuron signs).

5.3.1.1.9 12-Lead Electrocardiogram

Procedure

A 12-lead resting electrocardiogram (ECG) will be obtained at the times indicated in the Study Activities Table ([Appendix C](#)). For visits in which both ECGs and blood sample(s) are collected, ECGs should be obtained prior to any blood collection. ECGs will be recorded after the subject has been supine for at least 5 minutes. The subject should be instructed to remain completely stationary during the recording, without talking, laughing, deep breathing, or swallowing during the time of recording (10 seconds). The ECG measurements obtained on Day 1 will serve as the baseline for clinical assessment.

The ECGs will be read by a qualified local physician for an immediate safety assessment and also by the central reader who will provide a full report to the site within approximately 3 business days.

ECGs will be collected as single ECGs as follows:

- **Day 1 (Dose 1)**
 - Pre-dose (just prior to pre-infusion PK sample collection and the start of infusion)

- **Weeks 12, 24, 52, 104, 156, 208, and 260**
 - Pre-dose (just prior to the start of infusion, when applicable [no dose at Week 260])

Local ECG Reading:

A qualified physician at the study site will interpret and document his/her global interpretation on the ECG tracing, based on the following conventions, as appropriate:

- Normal ECG
- Abnormal ECG – not clinically significant
- Abnormal ECG – clinically significant

This physician will sign and date the ECG tracings. Each ECG should be reviewed by the physician before study drug administration to ensure the tracing is interpretable and no acute, medically serious condition is present. The investigator's (or physician designee's) initial interpretation of the ECG will be the basis of any decisions related to the study conduct and treatment of the study subjects (e.g., eligibility at Baseline, adverse event assessment).

Central ECG Reading:

Site personnel will transmit ECG data to an ECG central laboratory for central processing and reading by a qualified cardiologist (central reader) who will independently review each ECG. QT interval corrected for heart rate (QTc) will be determined using Fridericia's correction method (QTcF). The central ECG laboratory's data will be entered into the database. The central reader will also provide the interpretation of the ECG (i.e., "Normal" or "Abnormal"). The central ECG laboratory will send the ECG report to the site within approximately 3 business days. The Investigator (or physician designee) will review the central reader's report/assessment and document his/her review by signing and dating the central ECG laboratory report. The investigator should review and reconcile if necessary his/her interpretation of the ECG (normal/abnormal) with the

central ECG laboratory in case of relevant divergent assessments and reconcile as he/she determines is appropriate.

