5.0 Investigational Plan

5.1 Overall Study Design and Plan: Description

Overview

Study M15-563 is a long-term extension of Study M15-562, a Phase 2, randomized, multiple-dose, multicenter study in subjects with PSP. Subjects who completed the 52-week Treatment Period in Study M15-562 and meet all entry criteria will be eligible for enrollment into Study M15-563. Study M15-562 was designed to randomize 378 subjects to meet scientific and regulatory objectives without enrolling an undue number of subjects in alignment with ethical considerations. Therefore, the number of subjects who will participate in Study M15-563 will be up to the number of subjects enrolled in Study M15-562 (the actual number of subjects who enroll in Study M15-563 will depend on the number of subjects from Study M15-562 who are eligible and consent to rollover). The study will be conducted at approximately 60 multinational sites.

Study M15-563 will consist of a treatment period of up to 5 years and a post-treatment follow-up visit approximately 20 weeks after the last dose of study drug (including subjects who prematurely discontinue treatment). All subjects will receive ABBV-8E12 as follows: 1) subjects who received placebo in Study M15-562 will be randomized, in a

1:1 ratio, to 1 of 2 ABBV-8E12 doses (2000 or 4000 mg); and 2) subjects who received ABBV-8E12 2000 or 4000 mg in Study M15-562 will continue on the same dose. Refer to Section 5.5.3 for detailed information on randomization. Investigators and subjects will remain blinded to the treatment assignments in Study M15-562 and will be blinded to the dose level of ABBV-8E12 in Study M15-563.

Subjects from Study M15-562 will complete baseline procedures and receive the first infusion of study drug on Day 1 of Study M15-563. For subjects who do not have interruptions in study drug administration between Study M15-562 and Study M15-563 (i.e., the duration between the last dose of study drug in Study M15-562 and the first dose of study drug in Study M15-563 is no more than 45 days), procedures that were performed at the Week 52 Visit in Study M15-562 do not need to be repeated for the Day 1 Visit in Study M15-563. Week 52 procedures from Study M15-562 cannot be used to satisfy the Day 1 requirements for Study M15-563 if more than 45 days (but less than 8 weeks) have elapsed since the subject's last dose of study drug in Study M15-562; in that case, Day 1 activities for Study M15-563 must be performed.

[figure not shown]

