5.3.1.1.3 Physical Examination

Symptom-driven physical examinations will be performed at the times indicated in the Study Activities Table ([Appendix C](#)). Additional symptom-directed physical examinations will be performed when necessary. The physical examination performed on Day 1 prior to the first dose will serve as the baseline physical examination for clinical assessment. Any significant physical examination findings after dosing will be recorded as adverse events.

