6.1.4 Adverse Event Collection Period

All adverse events reported from the time of study drug administration until 20 weeks following discontinuation of study drug administration have elapsed (approximately 5 half-lives) will be collected, whether solicited or spontaneously reported by the subject.

In addition, SAEs and protocol-related nonserious adverse events will be collected from the time the subject signed the study-specific informed consent.

Adverse event information will be collected as shown in [Figure 2](#).

Figure 2. Adverse Event Collection

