8.1.2 Safety Analyses

Comparisons between treatment groups (Studies M15-562/M15-563) of interest will be performed with a 2-sided test at the significance level of 0.05 unless otherwise specified.

Unless otherwise specified, treatment group differences in continuous safety variables (e.g., change from Baseline to final observation on laboratory tests) will be assessed using an analysis of variance (ANOVA) model with treatment group as the main effect, and the treatment group differences in binary safety variables will be evaluated using Fisher's exact test.

A treatment-emergent adverse event (TEAE) is defined as any adverse event that begins or worsens in severity on or after the date of the first dose of study drug and no more than 20 weeks after the date of the last dose of study drug.

All other safety assessments that are taken no more than 45 days after the last dose of study drug will be included in the safety evaluation of the Treatment Period, and all safety

assessments that are taken more than 45 days but not more than 20 weeks after the last dose of study drug will be included in the safety evaluation for the Post-treatment Follow-up Visit.

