5.0 Analysis Populations

5.1 Analysis Data Sets

Data Sets for Efficacy Analyses

Two data sets will be created for the efficacy analysis: an intent-to-treat (ITT) data set and a delayed-start data set.

ITT Data Set: the ITT data set consists of all subjects who received any dose of study drug in Study M15-563. All efficacy analyses will be conducted on the ITT data set using data from Study M15-563 alone unless otherwise specified.

Delayed-Start Data Set: The Delayed-Start data set includes all subjects from the Study M15-562 ITT data set who received placebo or ABBV-8E12 in Study M15-562 regardless of whether they enroll in Study M15-563 or not. For the Delayed-Start analysis, efficacy data for PSPRS total score from both Study M15-562 and Study M15-563 studies will be included.

Data Sets for Safety Analyses

The safety data set will consist of all subjects who received any dose of study drug infusion in Study M15-563. For safety analyses, the actual treatment received will be used instead of the treatment assignment at enrollment. There are two safety data sets: a Stand-Alone data set and a Cumulative data set.

Stand-Alone Data Set: The Stand-Alone data set is the primary data set for safety analyses, and will contain data from Study M15-563 only, regardless of the treatment received in Study M15-562. Baseline for the Stand-Alone data set will be the last observation on or before the first dose of ABBV-8E12 in Study M15-563. If no Baseline is recorded in Study M15-563, the last value in Study M15-562 will be used as the Baseline.

Cumulative Data Set: The Cumulative data set will consist of data from both Study M15-562 and Study M15-563. It is the secondary data set for safety analyses. For subjects who were in the placebo group in Study M15-562, their safety data from Study M15-562 will not be included in the Cumulative data set but their safety data from Study M15-563 will be included. For subjects who were in the placebo group in Study M15-562, Baseline will be the last observation prior to the first dose of study drug in Study M15-563. For subjects who were in ABBV-8E12 treatment groups in Study M15-562, Baseline for the Cumulative data set will be their Baseline in Study M15-562.

Data Sets for Biomarker Analyses

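### Protocol 5.3.1.1.8 assigns neurological symptoms to M15-562 or M15-563 by calendar day, not by the first infusion, in conflict with 6.1.4 and the TEAE definition

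*Protocol*

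**What the plan says.** Protocol 5.3.1.1.8 (Neurological Examination) first fixes the baseline: "The neurological exam performed on Day 1 will serve as the baseline for clinical assessment". It then divides symptoms between the two studies: "Symptoms identified on Day 1 will be recorded as adverse events for Study M15-562", whereas "new symptoms or current symptoms that change in severity or frequency after Day 1 will be recorded as adverse events for Study M15-563". Neither part mentions the infusion.

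The corresponding sentence for the physical examination, in 5.3.1.1.3, does state the timing: "The physical examination performed on Day 1 prior to the first dose will serve as the baseline physical examination". Sections 5.3.1.1.4 (orthostatic vital signs), 5.3.1.1.9 (ECG) and 5.3.1.1.10 (laboratory baseline) also place the baseline before dosing.

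The general adverse event rules use different starting points. Section 6.1.4 collects "All adverse events reported from the time of study drug administration until 20 weeks following discontinuation of study drug administration", and adds that SAEs and protocol-related nonserious events are collected from informed consent. Protocol 8.1.2 defines a TEAE as an event that "begins or worsens in severity on or after the date of the first dose of study drug", within 20 weeks of the last dose; SAP 10.2 has the same definition.

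There are two safety data sets. The Stand-Alone set is primary and holds M15-563 data only. The Cumulative set combines both studies but, for M15-562 placebo subjects, "their safety data from Study M15-562 will not be included in the Cumulative data set" (SAP 5.1; Protocol 8.0 agrees).

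**The concern.** The split in 5.3.1.1.8 falls at the end of a calendar day, while the exposure that matters begins during that day. For placebo-start subjects the Day 1 infusion is the first exposure to the antibody. Protocol 6.1.7.5 says subjects will be closely monitored for events suggesting neurotoxicity, so an early neurological symptom is one the safety tables should hold.

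The TEAE definition cannot recover an event filed under the other study if the analysis set does not draw on that study's data. At stake is whether non-serious neurological symptoms arising on the day of the first infusion appear in the M15-563 safety tables.

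**Working it through.** The plan gives no figure to reproduce. The check has three steps.

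**1. Can a post-infusion symptom be identified on Day 1?** Yes.
- Protocol 5.1 keeps subjects on site for at least 30 minutes after each infusion. Section 5.3.2.1.1 takes Day 1 PK samples up to 2 hours after the infusion ends.
- Infusion rates are 3.5 to 4.7 mL/min (5.5.1). The volume is assumed to be 500 mL: Table 4 gives this for the saline, and 5.5.2.3 says placebo and active volumes are essentially identical.
- Infusion time = volume / rate: 500/4.7 = 106 min and 500/3.5 = 143 min.
- Adding 120 min for PK sampling gives 226 to 263 min, or about 3.8 to 4.4 hours on site from the start of the infusion.

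**2. Each type of event taken through the three rules**

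| Event | 5.3.1.1.8, read literally | 6.1.4 | TEAE definition | Result |
|---|---|---|---|---|
| Neurological symptom with onset before Day 1, found at the Day 1 examination | M15-562 | Before M15-563 collection starts | Not treatment-emergent | Agree |
| Neurological symptom starting or worsening on Day 1 after the infusion starts | M15-562 | M15-563 | Treatment-emergent | Conflict |
| Neurological symptom starting on Day 1 before the infusion | M15-562 | Not M15-563, unless serious or protocol-related | Treatment-emergent, because the rule goes by date | Conflict in the other direction |
| Neurological symptom starting after Day 1 | M15-563 | M15-563 | Treatment-emergent | Agree |
| Non-neurological event on Day 1 after the infusion starts | Not clearly covered | M15-563 | Treatment-emergent | No clear conflict |

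The third row shows that moving to the date of first dose would not be enough. Section 6.1 names only the date of onset, and a date cannot separate the hours before the infusion from those after it.

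**3. Where a second-row event goes if it is filed under M15-562**
- Placebo-start subject: absent from Stand-Alone (M15-563 data only) and absent from Cumulative (M15-562 data dropped).
- Early-start subject: absent from Stand-Alone, but still in Cumulative through its M15-562 part.

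If the same event is filed under 6.1.4, it appears in both sets for both kinds of subject.

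**The case against.** The strongest reply is that the sentence means symptoms found at the baseline examination, so no post-infusion symptom is in view. It directly follows the sentence making that examination the baseline. Protocol 5.1 puts baseline procedures before the first infusion. It also says, for dosing gaps of up to 45 days, that "procedures that were performed at the Week 52 Visit in Study M15-562 do not need to be repeated for the Day 1 Visit", so the examination may in fact be the parent study's Week 52 one, which would explain filing its findings there. Section 6.1.4 is also the section that governs collection, and a site might reasonably follow it. This is probably the intent, and it stands as a reason to treat the loss as a risk rather than a certainty. It does not remove the contradiction: the text refers to the day rather than the examination, and its counterpart is after Day 1 rather than after the first dose.

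Other safeguards also narrow the point:
- Under 6.1.4, SAEs and protocol-related events are collected from consent, which precedes Day 1 dosing.
- The DMC is unblinded and may see all data it needs (5.5.5).
- SAP 10.1 plans no treatment comparisons, so descriptive incidence is affected, not a test.
- Figure 2 and Section 6.1.5 were not available for this review and might clarify the cut-point.

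A reader might infer that first-dose reactions in general are sent to the M15-562 placebo arm. The documents do not support that. The sentence concerns neurological symptoms; infusion and allergic reactions fall under the general rules. How M15-562 would count such an event depends on that study's own collection window and TEAE rule, which are not given here.

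**Conclusion.** The contradiction is real and should be corrected. Section 5.3.1.1.8 conflicts with 6.1.4 and with the TEAE definition for neurological symptoms that start or worsen on Day 1 after the infusion starts. Read literally, it removes non-serious events of this kind from both safety sets for placebo-start subjects, and from the primary set for early-start subjects.

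That consequence assumes that a site applies 5.3.1.1.8 over 6.1.4 and that neither Figure 2 nor Section 6.1.5 settles the matter. The number of events cannot be determined, because the documents give neither a Day 1 neurological event rate nor the number of placebo-start subjects. A reader might also infer a directional bias, with too few events on drug and too many on placebo; without the M15-562 rules that cannot be established.

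**What to change.** Reconcile 5.3.1.1.8 with 6.1.4 on one cut-point, the start of the first M15-563 infusion:
- State that the Day 1 neurological examination, or the Week 52 examination standing in for it, is done before that infusion.
- Record symptoms present before the infusion starts for M15-562, except SAEs and protocol-related events after M15-563 consent, which stay with M15-563 under 6.1.4.
- Record symptoms that start or worsen at or after the start of the infusion, including later on Day 1, for M15-563.
- For adverse events with onset on Day 1, add an eCRF item giving onset as before or after the infusion start, or a clock time. The treatment-emergent flag for that date can then use it.

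The cost is a short protocol edit, matching eCRF guidance and one extra data item for Day 1 events. The infusion start is already recorded to the nearest minute (5.5.1). Only recording and the stated timing of the examination change; clinical management does not.

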5.3.1.1.10 Clinical Laboratory Tests

Samples will be obtained at a minimum for the clinical laboratory tests listed in [Table 2](#) at the times indicated in the Study Activities Table ([Appendix C](#)).

A certified laboratory will be used to process and provide results for the clinical laboratory tests. Central Laboratory reference ranges will be provided prior to initiation of the study. The baseline laboratory test results for clinical assessment for a particular test will be defined as the last measurement prior to the initial dose of study drug.

Table 2. Clinical Laboratory Tests

Hematology	Clinical Chemistry	Urinalysis
Hematocrit	BUN	Specific gravity
Hemoglobin	Creatinine	Ketones
RBC count	Total bilirubin	pH
WBC count	Albumin	Protein
Neutrophils	AST	Glucose
Bands (if detected)	ALT	Blood
Lymphocytes	ALP	Microscopic examination, if dipstick results are positive
Monocytes	Sodium	CSF Basic Laboratory Tests^c
Basophils (if detected)	Potassium	
Eosinophils (if detected)	Calcium	RBC, WBC with differential
Platelet count (estimate not acceptable) ^a	Inorganic phosphate	Total protein
MCV	Uric acid	Albumin
MCHC	Cholesterol	Glucose
PT	Total protein	
aPTT ^b	Glucose	
PT/INR ^b	Triglycerides	
	Bicarbonate/CO ₂ chloride	

ALP = alkaline phosphatase; ALT = alanine aminotransferase; aPTT = activated partial thromboplastin time; AST = aspartate aminotransferase; BUN = blood urea nitrogen; CSF = cerebrospinal fluid; CO₂ = carbon dioxide; INR = international normalized ratio; MCHC = mean corpuscular hemoglobin concentration; MCV = mean corpuscular volume; PT = prothrombin time; RBC = red blood cell; WBC = white blood cell

- Platelet count results to be reviewed by the investigator before lumbar puncture.
- Coagulation results to be reviewed by the investigator before lumbar puncture.
- To be done at the local laboratory. If the local laboratory is unable to perform some of the CSF measurements, samples may be sent to the central laboratory for analyses of total protein, albumin, and glucose only.

For any laboratory test value outside the reference range that the investigator considers to be clinically significant:

- The investigator will repeat the test to verify the out-of-range value.
- The investigator will follow the out-of-range value to a satisfactory clinical resolution.
- A laboratory test value that requires a subject to be discontinued from the study or requires a subject to receive treatment will be recorded as an adverse event.

For all laboratory abnormalities the investigator will determine if they indicate a new disease process, an exacerbation or worsening of an existing condition, or require further action to be taken and therefore need to be reported as adverse events. Accordingly, for any values outside of the reference range, the Investigator will indicate on the report if the result is Clinically Significant (CS) or Not Clinically Significant (NCS). If a laboratory abnormality meets criteria for a Potentially Clinically Significant (PCS) laboratory value, as defined in [Appendix D](#), the investigator must either report an associated adverse event or document in source the reason(s) the finding was not considered an adverse event.

Any laboratory value that remains abnormal at Premature Discontinuation/End of Study and was judged to be clinically significant will be followed according to accepted medical standards until resolution of the abnormality.

